Facebook may be an efficient platform for delivering evidence-based weight loss programming to post-partum women. Facebook is currently the most popular online social network,²⁰ used by 81% of online moms.²¹ 70% of Facebook users engage daily, including 43% multiple times per day,²² for upwards of 50 minutes a day.²³ Many women seek support about health and parenting from their Facebook network.^{21,24} Interactions via Facebook are frequent, brief, and asynchronous, with women seeking support when they need it. Delivering interventions via Facebook allows us to connect with post-partum women where they are, more fully integrating into their lives and daily routines. Weight loss interventions that use Facebook appear promising.²⁵⁻²⁷

We have developed a post-partum weight loss intervention based on the Diabetes Prevention Program,²⁸ tailored to needs of post-partum women and for delivery via Facebook. Participants receive counseling from a coach through posts and discussions via a private Facebook group. We conducted a one-arm pilot study of this intervention with 19 overweight or obese women (95% retention). Average weight loss was 4.8% (SD: 4.2%), and 58% achieved clinically significant weight loss (i.e., $\geq 5\%$).^{29,30} 88% said they would be likely/very likely to participate again if they had another baby, and 82% would recommend the program to a post-partum friend. While delivering the intervention via Facebook offers many advantages, we have no reason to believe it will be more efficacious than a traditionally-delivered intervention (i.e., via in-person group sessions), especially when intervention content is identical. Instead, we hypothesize that in a large trial delivery via Facebook will be at least non-inferior for weight loss compared to in-person delivery, but superior in cost-effectiveness.

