Design, Procedures, Materials and Methods: [Describe the study design, including the sequence and timing of all study procedures. Experimental procedures should be clearly described and labeled as such. If the study uses control or experimental groups, or different treatment arms, clearly describe what participation will be like for each of the groups or study arms. Tip: describe procedures in the order conducted. The IRB strongly suggests that investigators incorporate *flexibility* into the study design to accommodate anticipated events (i.e. explain how missed study appointments can be made up by participants). If the research involves study of *existing samples/records*, describe how authorization to access samples/records will be obtained. If the study involves use of *deception* explain the reason why this is necessary. If applicable, describe the use of audiotape and/or videotape and provide justification for use. If this study offers treatment for the participants’ condition, complete the Treatment Study Supplemental Form (IRB-1C) and attach it to this application for review. If the study includes *measures, survey instruments and questionnaires*, identify each and, if available, provide references for the measures. Describe what they intend to measure (relate to purpose/hypothesis) and their psychometric properties (e.g., reliability and validity). Identify any that were specifically created for the study.]

Participation will include a baseline assessment, an orientation webinar, participation in a 6-month weight loss intervention, and follow-up assessments at 6 and 12 months. Study visits and in-person treatment sessions will take place in a private space (such as a conference room, exam room, or classroom) at UConn Storrs, UConn Hartford, the Hartford Public Library, Hartford Hospital, Women’s Ambulatory Health Services, or WIC offices. Overall, it is estimated that completing study assessments will take approximately 5-6 hours and participating in treatment sessions (in-person condition) or engaging with

the counselor and other participants online (Facebook condition) will take approximately 90 minutes per week over the 6-month intervention period.

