Baseline assessment. Staff will call and/or email participants within 3 days of their scheduled baseline assessment to remind them of the appointment. The baseline assessment will include informed consent measurement of height and weight, completion of a contact information sheet, and completion of additional measures which will be used to determine eligibility (screeners for depression and binge eating disorder). Study personnel will also help participants download My Fitness Pal app (all) and an app to track time on Facebook (Android users) and provide instruction of how to use these apps. For iPhone users, personnel will also show them how to locate Facebook app usage data using the battery settings. We expect the baseline study visit to take 30-45 minutes. Following the baseline assessment, research staff will fax the medical clearance form to participants' primary care provider or OBGYN. After the baseline visit, staff will email participants a link to complete a survey via REDCap. A copy of the baseline survey is enclosed. We will email participants a \$20 gift card after they have completed the baseline visit and online survey.

Orientation Webinar. Participants will complete a 60-minute orientation webinar. The purpose of the webinar is to educate participants about what research is, review study procedures, review importance of participation of enrolled participants, and to allow participants another opportunity to evaluate if joining this study is the right choice for them. This webinar is being conducted to improve study retention. The webinar moderator will record in REDCap tracking which participants completed the webinar.

Pre-Randomization Survey. Following the orientation webinar, we will email participants a short online survey that includes Facebook time measures and completion of a randomization agreement. We will email participants a copy of the randomization agreement form for their records. A copy of the pre-randomization survey is enclosed.

Participants will need to complete the telephone screening, baseline assessments (visit and survey), and orientation webinar, and pre-randomization survey before being randomized.

Randomization. We will randomize participants 1:1 to the FB and IP conditions in randomly permuted blocks of size 4 and 6. Randomization will be stratified by weeks post-partum at enrollment (8 weeks to <6 months, 6-12 months) and smartphone type (iPhone vs Android) .

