Weight loss intervention. The 6-month intervention will include dietary and exercise counseling and tips to help participants meet their healthy lifestyle goals. Participants will receive personalized calorie and physical activity goals to help them achieve a healthy weight loss of 1-2 pounds per week. Breastfeeding women will receive daily calorie goals that will facilitate weight loss while accounting for energy needs to support lactation; weight loss expectations do not differ by breastfeeding status. Participants will be encouraged to increase physical activity to 150 minutes per week of moderate intensity activity. While we will provide information about specific exercises designed to help with recovery from childbirth (e.g., pelvic floor exercises), participants will not be required to engage in any particular exercises or activity program. Counselors will encourage and support participants to make a plan for incorporating regular physical activity into their lives in a way (i.e., duration per session, frequency per week) that works for that individual woman. We will encourage participants to track their diet and exercise daily. We will encourage participants to use My Fitness Pal to track their diet and activity. In the in-person condition, the intervention will be delivered via weekly 90-minute group meetings for the first four months and then every other week in months 5 and 6. In the Facebook condition, the intervention will be delivered via a secret (private) Facebook group. See section 3.D.2.2.9 (3.D.2.2.9.1 through 3.2.2.9.6; pages 9-10) of the enclosed grant application for more details on the interventions.

Due to weather or to prevent spread of illness (e.g., coronavirus), we may hold intervention meetings for the in-person condition via video or telephone conference call.

Weekly time survey. Weekly, participants in both treatment conditions will complete a brief online survey to report current weight and time spent on Facebook. We expect the survey to take less than 5 minutes. The survey will be administered via REDCap. A copy of the weekly survey is enclosed.

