Aim 3: Measuring time on Facebook. We will compare self-reported time spent on Facebook to participate in the intervention with application-tracked time on Facebook, changes in use, and time spent visibly engaging, to develop procedures for measuring time that balance accuracy and participant burden. We will compare self-reported time spent on Facebook to participate in the intervention with (1) application-tracked time spent on Facebook, (2) change in application-tracked time over the intervention, and (3) estimated time spent visibly engaging in the intervention using paired t-tests and Wilcoxon rank-sum tests, as appropriate. We will also examine accuracy in reporting total time on Facebook at baseline and adjust self-reported time spent on Facebook to participate in the intervention accordingly. From these comparisons, we will develop procedures for measuring time spent on Facebook to participate in the intervention that maximize accuracy while not placing undue burden on participants nor changing their behavior as a result of surveilling their social media activities.

Inclusion/Exclusion Criteria: [List ALL inclusion and exclusion criteria. Any proposed exclusion criterion based on gender (women of childbearing potential), age, or race must include justification for the exclusion. Describe the conditions under which participants may be removed from the study, i.e., noncompliance with study rules, study termination, etc.]

Only women will be included as the aim of this study is to refine a post-partum weight loss intervention.

Inclusion criteria. Women aged ≥ 18 years, 8 weeks to 12 months post-partum at enrollment, overweight or obese ($BMI \geq 25$ kg/m²) per measured height and weight at the baseline visit, owns a scale (we will provide women with a scale if needed), comfortable reading and speaking English, owns an iPhone or Android smartphone, active Facebook user as defined as daily Facebook use and posts/comments at least weekly over the past 4 weeks, clearance from primary care provider or obstetrician/gynecologist, willing and able to participate in either treatment condition (Facebook or in-person), available to attend in-person meetings over the 6-month study period in Hartford, CT, 45 minutes or less to travel to intervention meetings, and willing and able to provide informed consent.

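### Aim 3's comparison with change in tracked Facebook time cannot separate self-report error from a change in use shared by both arms; the in-person arm's Facebook time should be analysed beside it

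*Protocol*

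**What the plan says.** The Aim 3 paragraph of the Protocol's Data Analysis section begins: "We will compare self-reported time spent on Facebook to participate in the intervention with (1) application-tracked time spent on Facebook". The second yardstick is listed as "2) change in application-tracked time over the intervention", and the third is an estimate of time spent visibly engaging. The methods named are paired t-tests and Wilcoxon rank-sum tests. One adjustment is described: accuracy in reporting total Facebook time at baseline is used to correct self-reported intervention time. The in-person arm is not mentioned. The SAP, under feasibility of assessment procedures, undertakes to work out how Facebook time should be measured but adds no analysis.

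The design sections collect more than this analysis uses:

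- Baseline assessment: before allocation, Android users install a tracking app and iPhone users are shown where their Facebook usage data sit.
- Pre-Randomization Survey: "we will email participants a short online survey that includes Facebook time measures".
- Randomization: "We will randomize participants 1:1 to the FB and IP conditions", stratified by time since delivery and phone type.
- Weekly time survey: "Weekly, participants in both treatment conditions will complete a brief online survey to report current weight and time spent on Facebook".
- Potential Harms/Risks and Inconveniences: Android users report their Facebook time throughout the study, with no restriction to one arm.

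**The concern.** A change in tracked Facebook time measures intervention time only if the woman's other Facebook use stays level. Over six months it may not: infants get older, women may return to work, and tracking may itself alter use. Any such change that is common to both arms goes straight into the yardstick. If other use falls, an accurate self-report looks too high. If it rises, the same self-report looks too low.

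Aim 3 exists to settle how intervention time will be measured, and the SAP ties that to the cost-effectiveness aim of the later non-inferiority trial. A comparison that mixes misreporting with drift is weak evidence for that choice. The randomized in-person arm could separate the two, but no analysis of its Facebook time is stated.

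**Working it through.** The documents give no figure for Aim 3, so there is none to reproduce.

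**Algebra.** Let I be true intervention time on Facebook, e the self-report error, and c the change in other Facebook use common to both arms.

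- Self-report: S = I + e
- Change in the Facebook arm: I + c
- Change in the in-person arm: c
- Planned comparison: S − (I + c) = e − c
- With the in-person change subtracted: S − [(I + c) − c] = e

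The baseline-accuracy adjustment alters S, not the tracked change, so c remains. The other two yardsticks do not remove it either: total tracked time includes all other use, and visible engagement misses silent reading.

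Two further terms limit the contrast. Let d be intervention time that displaces other Facebook use, and k be Facebook time that in-person women spend seeking weight-loss support. The contrast then equals I − d − k. It removes c, does not recover d, and is diluted by k.

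**Inputs.** The Protocol background gives Facebook use "for upwards of 50 minutes a day", so 50 × 7 = 350 min/week; this describes Facebook users in general. The design section says participation "will take approximately 90 minutes per week over the 6-month intervention period". The sample size section gives 36 per arm; 80% of 36 is 28.8, taken as 29. Values of c and the SD of change are assumptions.

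**Size of the shift.**

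| Shared change | c (min/week) | Yardstick, 90 + c | Apparent error of an accurate self-report, −c | Relative to 90 |
|---|---|---|---|---|
| −20% | −70 | 20 | +70 | +78% |
| −10% | −35 | 55 | +35 | +39% |
| 0 | 0 | 90 | 0 | 0 |
| +10% | +35 | 125 | −35 | −39% |
| +20% | +70 | 160 | −70 | −78% |

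**How visible this would be.** The simulation used 3,000 runs with 36 women per arm, intervention time averaging 90 and self-report error with mean 0 and SD 20. With c = −35, the paired t-test is significant at 5% in about 91%, 38% and 20% of runs when the SD of other change is 60, 120 and 180. With c = −70 the figures are 100%, 92% and 62%. With c = 0 they are about 5%. After subtracting the in-person change, the mean discrepancy is within about 1 min/week of zero in every scenario.

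**Precision.** With the same SD in each arm, the 95% half-width is 1.96 × SD/√n for one arm and 1.96 × SD × √(2/n) for the contrast, a ratio of √2 ≈ 1.4.

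| SD | One arm, n = 36 | Contrast, 36 per arm | Contrast, 29 per arm |
|---|---|---|---|
| 60 | 20 | 28 | 31 |
| 120 | 39 | 55 | 62 |
| 180 | 59 | 83 | 93 |

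**Bias against variance.** The contrast removes a squared bias of c² and adds variance SD²/36. It therefore has the smaller root mean squared error only when |c| exceeds SD/6. At SD 100 that is 16.7 min/week (16.7/350 = 4.8%); at SD 150 it is 25 min/week (25/350 = 7.1%).

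**The case against.** Several stronger readings are tempting, and the documents do not support them.

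- A reader might infer that the plan excludes the in-person arm. It is silent rather than exclusive, and the within-arm reading follows from where intervention time on Facebook can exist. Nor does it define the period: the change could run from before to during the intervention, or from its start to its end. Shared change enters either way. The rank-sum test is a two-sample test, but no between-arm comparison is listed for it.
- A reader might infer that the Protocol concedes a surveillance effect, because it wants a procedure "nor changing their behavior as a result of surveilling their social media activities". That states a goal for the procedures to be developed. Tracking also starts at the baseline visit, so the measure before randomization may already reflect it. The other mechanisms are plausible, but the documents give them no direction or size.
- A reader might infer that a significant test would lead to a measure being dropped. No such rule exists. Aim 3 weighs three comparisons, baseline reporting accuracy and participant burden.
- A reader might infer that the contrast should replace the paired comparison. That would lose the pairing within each woman, and for small shared changes it would increase total error, as shown above.
- A reader might infer that all the data needed are already in hand. The documents do not show that the surveys record tracked rather than self-reported time, least of all for iPhone users.

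The simulation also puts the same shift into both arms, with no displacement or contamination, so subtraction is bound to work in it. It shows the consequence of a shared change, not that one will occur. All of this stands. What it leaves intact is that the stated comparison estimates e − c and nothing else in the plan removes c.

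**Conclusion.** The concern holds as a gap in one exploratory comparison of a pilot. The second Aim 3 comparison cannot separate self-report error from a change in Facebook use shared by both arms, and no stated analysis uses the in-person arm's Facebook time to do so. The bias is −c, whatever the SD. Its real size is unknown: the 39% in the 10% case rests on 350 min/week taken from Facebook users in general, on the planned 90 min/week, and on an assumed shift. The case for adding the contrast rests on the algebra and on randomization, not on the simulated rejection rates. It does not support discarding the planned comparison.

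**What to change.** Keep the paired comparison and add the following to Aim 3 in the Protocol and to the SAP.

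1. Define the period over which change is measured, and use the same period in both arms.
2. Report the in-person arm's mean change in Facebook time as the estimate of shared change.
3. Estimate the Facebook-minus-in-person difference in mean change with a 95% CI, adjusted for baseline Facebook time and the two randomization strata. Set mean self-reported intervention time in the Facebook arm against it.
4. Label this contrast net added Facebook time. Say that it misses displaced use and is diluted if in-person women seek weight-loss support on Facebook; the contamination data from Aim 1 help to judge the latter.
5. Confirm that the pre-randomization and weekly surveys capture tracked values in both arms and on both phone types, and use those values if so.

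The cost is a few lines of text and one extra model. On the documents' wording no new visits appear necessary, subject to item 5. The statistical cost is the wider interval shown above and a result that speaks to group means, not to individual women.

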The main purpose of the pilot trial is to examine the feasibility of recruitment (especially the proportion of women unwilling to be randomized to either condition), sustained participation, contamination, retention, and feasibility of assessment procedures, particularly measurement of cost-related data, in both treatment conditions, thus identifying modifications required before examining non-inferiority in a large randomized controlled trial. Leon, Davis, & Kraemer (2011) state "power analyses should not be presented in an application for a pilot study that does not propose inferential results."³¹ As they and others recommend,^{31,32} we based the sample size on necessities for examining feasibility, thus identifying modifications required to the design of the trial or study procedures before conducting the subsequent full-scale non-inferiority trial. Conducting two waves allows us to iteratively refine how we deliver intervention content via Facebook, and each wave includes n=36 women allows us to assess the feasibility of recruitment and engagement under the conditions of the subsequent trial. While we will aim to maximize retention in both conditions, with retention of $\geq 80\%$ to be acceptable, a priori, we decided that a retention rate in either condition lower than 60% would indicate that the non-inferiority trial is not feasible as designed. With n=36 per treatment condition, the 95% confidence interval (CI) for the estimated retention rate will be within $\pm 13\%$ if observed retention is 80%. Given n=36 per condition, the lower limit of the 95% CI for the observed retention rate in either treatment condition should not be lower than 60%.

We will enroll up to 125 participants with the intention of randomizing 72 participants. As the current study is a feasibility study, we are unsure the proportion of enrolled (consented) participants who will be randomized, as some participants will fail to complete baseline measures or may be found to be ineligible after baseline assessments.

For EACH Participant Population State Describe the Study Population(s): [Describe the participant population(s) including gender, ethnicity, income, level of education and age range.]

All participants will be adult women (aged 18 years or older). We anticipate minority enrollment of at least 30% as expected by the NIH/NHLBI. We are not targeting enrollment by income or level of education; we aim to recruit a diverse sample with respect to these characteristics.

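### Aim 3 names only tests for a shift in location, one of them for unpaired data, so its analysis cannot show how accurately time on Facebook is measured

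*Protocol*

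**What the plan says.** The Protocol gives the purpose of Aim 3 as "to develop procedures for measuring time that balance accuracy and participant burden". The Data Analysis section (Aim 3) sets self-reported intervention time against three comparators. The first two are "1) application-tracked time spent on Facebook, (2) change in application-tracked time over the intervention". The third, with the only statistics named, is "3) estimated time spent visibly engaging in the intervention using paired t-tests and Wilcoxon rank-sum tests, as appropriate".

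The use of the results follows: "From these comparisons, we will develop procedures for measuring time spent on Facebook to participate in the intervention that maximize accuracy". A separate step precedes it: "We will also examine accuracy in reporting total time on Facebook at baseline and adjust self-reported time spent on Facebook". No statistic or adjustment method is given for that step.

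The data come from repeated reports: "Weekly, participants in both treatment conditions will complete a brief online survey to report current weight and time spent on Facebook". The Protocol does not say how the weekly values are reduced for analysis.

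The SAP (Feasibility of assessment procedures) states the goal of developing time-measurement procedures, next to the cost data for the later trial. It names no test or agreement statistic. For Aim 3, neither document names limits of agreement, an intraclass or concordance coefficient, an absolute error or an acceptable error. The inter-rater reliability under Aim 2 concerns qualitative coding.

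**The concern.** Whether a self-report is accurate is a question about bias and spread relative to a reference. A paired t-test asks only whether the mean difference could be zero. Two problems follow.

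- A large p-value is weak evidence of accuracy. It can arise because over- and under-reports cancel, or because the sample is too small to see a real bias.
- A small p-value need not mean a poor measure. When the differences are tight, a trivial offset is significant.

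The rank-sum test adds a separate fault. It treats the two columns as independent groups and discards the pairing, so large differences between women swamp differences within a woman.

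The SAP links the time measure to the cost-effectiveness aim of the later non-inferiority trial. If Aim 3 delivers only p-values, the investigators will not know the size of the bias, the spread around it, or whether either is tolerable.

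**Working it through.** Aim 3 states no sample size, alpha or error limit, so there is no planned figure to reproduce. The check is on how the named tests behave.

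**Inputs from the documents**
- n: "With n=36 per treatment condition" (Justification of Sample Size). Self-reported intervention time on Facebook concerns the Facebook condition, so n is at most 36. At the 80% and 60% retention levels in that section, 0.80 × 36 = 28.8 (29) and 0.60 × 36 = 21.6 (22).
- Expected use: about 90 min/week (Design section).

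**Assumptions, not in the documents**
- Two-sided alpha 0.05, and normal differences with the biases and SDs shown below.
- For the simulations: true time with mean 90 and between-woman SD 45 min/week, truncated at zero.
- One pair per woman.

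**Paired t-test.** The noncentrality is δ = (bias/SD) × √n, and P(significant) = P(|T| > t) for a noncentral t with n − 1 df. At n = 36, t = 2.030.
- Bias 0, SD 60: δ = 0, so P = 0.05 at any n.
- Bias 20, SD 60: δ = (20/60) × 6 = 2.00, P = 0.49.
- Bias 5, SD 8: δ = (5/8) × 6 = 3.75, P = 0.95.
- Bias 5, SD 10: δ = (5/10) × 6 = 3.00, P = 0.83.

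**Limits of agreement** = bias ± 1.96 × SD.

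| Bias, SD (min/week) | P(sig), n=36 | n=29 | n=22 | Limits (min) |
|---|---|---|---|---|
| 0, 60 | 0.05 | 0.05 | 0.05 | −118 to +118 |
| 20, 60 | 0.49 | 0.41 | 0.32 | −98 to +138 |
| 5, 8 | 0.95 | 0.90 | 0.80 | −11 to +21 |
| 5, 10 | 0.83 | 0.74 | 0.61 | −15 to +25 |

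In the first row, 2 × P(Z > 30/60) = 62% of women are off by more than 30 min. In the third row it is about 0.1%, from P(Z > 25/8) + P(Z < −35/8). The t-test is usually silent on the first case and usually significant on the third.

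**Rank tests on the same pairs** (simulated, n = 36, 4,000 runs per case)

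| Bias, SD | Rank-sum significant | Signed-rank significant |
|---|---|---|
| 0, 60 | about 1% | about 5% |
| 20, 60 | about 20% | about 47% |
| 5, 8 | about 0% | about 94% |

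Signed-rank tracks the paired t-test; rank-sum does not. For the 5-min offset, the two tests offered as alternatives give near-opposite answers on the same data.

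**Precision of the proposed replacement.** The SE of a limit is about SD × √(1/n + 1.96²/(2(n − 1))). At n = 36 the factor is √(0.0278 + 0.0549) = 0.2875. With SD 60 the 95% CI on each limit is ±1.96 × 60 × 0.2875 = ±34 min; with SD 8 it is ±4.5 min. These are imprecise but enough to tell the two cases apart.

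**The case against.** Several stronger readings are tempting, and the documents do not support them.

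- **That a noisy measure passes and a precise one fails.** The Protocol gives no alpha and no rule linking a p-value to acceptance. It says only that procedures will be developed from the comparisons, weighing accuracy, burden and changes in behavior. Nor does the second half hold for both named tests: rank-sum almost never flags a small offset.
- **That accuracy must mean accuracy for each woman.** The Protocol does not say so. If the later use is mean time per arm, mean bias matters most and cancelling errors cost only precision. With independent errors, the mean squared error of an arm mean is 3600/n for bias 0, SD 60 and 25 + 64/n for bias 5, SD 8. These are equal at n = 3536/25, about 141 per arm; above that, the noisier measure does better. So a wrong ranking of measures is not established for that use. This strengthens the case for estimating bias with a CI, since the paired t-test misses a 20-min bias about half the time.
- **That weekly pairs would be pooled as independent.** That could inflate false positives badly, but neither document proposes it. The handling is simply unstated.
- **That the plan ignores systematic misreporting.** It does not. The baseline check and adjustment could remove a constant offset, though no method is given and it cannot remove random error.

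One objection limits the remedy. Limits of agreement describe reporting error only when both measures target the same quantity. Total tracked time includes Facebook use outside the intervention, and visible engagement omits reading without reacting. Only total self-reported versus total tracked time at baseline clearly compares like with like.

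Finally, this is a pilot and the raw data remain available, so agreement statistics could be added later. That is so, but the tolerance is only credible if set before the results are seen.

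**Conclusion.** The point holds in this form: the only statistics named for Aim 3 test for a shift in location, and they cannot support a choice of procedure on accuracy. This follows from what the tests do and needs no assumed numbers. The naming of rank-sum for paired data is a plain error in the text.

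The sizes are illustrative. They rest on assumed biases, SDs and alpha, and for rank-sum on an assumed between-woman SD of 45 min. They move with n and SD: a 5-min offset is flagged by the paired t-test in 95% of trials at SD 8 and n = 36, but in 61% at SD 10 and n = 22. The harm is an analysis that cannot answer its question, not a stated decision rule that fails. The plan should be changed here, but the point does not touch the Aim 1 retention target or participant safety.

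**What to change.** Amend Aim 3 and carry it into the SAP, which now states only the goal.

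1. **Baseline, total self-reported versus total tracked time.** Report the mean difference with 95% CI and Bland-Altman limits of agreement with their CIs, on the log scale if error grows with use. Base the planned adjustment of self-report on this estimate and state its form.
2. **The three comparisons with self-reported intervention time.** Report the mean paired difference with 95% CI and the spread of the differences. Label these as including differences in definition (non-intervention use, reading without reacting), not only reporting error.
3. **Weekly data.** Use one mean per woman, or a mixed model with a random woman effect.
4. **Tests.** If a non-parametric test is kept, replace rank-sum with signed-rank.
5. **Choice of procedure.** Set a tolerable error in advance. Judge bias and spread against it, beside each measure's completion rate, to serve the stated goal to "develop procedures for measuring time spent on Facebook to participate in the intervention that maximize accuracy while not placing undue burden on participants". Do not choose on p-values.

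The cost is a few lines of SAP text and some extra SAS code, with no new data. The downside is that limits from about 36 women are imprecise (about ±34 min per limit if the SD is 60), so their CIs should be shown.
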